**Data analysis:**

The quantitative variables will be expressed as Mean (M) and Standard Deviation (SD), including range, minimum and maximum values. Apart from the simple description of data and variables, inferential analysis will be done to determine possible significant relationships and correlations between study variables or that allows to the contrast of hypothesis.

Shapiro Wilk and/or Kolmogorov – Smirnov will be applied to determine if the sample meets with the normal distribution criteria, and to decide the type of statistical test that will be implemented (parametric or no-parametric).

The T- student paired test or the U-Mann Whitney will be applied to establish the possible differences of means, according different dicotomic variables, in the assessment scales of FIM, PIADS, Walk tests and level of matching person – AT. The ANOVA test or Kruskal – Wallis will be used in the cases of polycotomic variables, to establish possible differences of means between results of the scales.

The association of numeric variables will be analysed by Pearson or Spearman correlation test, according to distribution of the sample. To evaluate the association of categorical variables, chi-square will be applied, or likelihood ratio if the observed frequencies are lower than 5%.

To check the differences between related samples, with repeated measures (in the case of FIM scale and the scales of mobility – initial assessment and in the follow-up of 2 and 6 months), the t-student test or the Wilcoxon ranges will be used, according correspond to the sample distribution.

The analysis of the data will be done with the program SPSS v.24 for Windows. The level of significance to do the contrast of hypothesis is established to 5%.

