#### **4. Methodology**

**Design:** Pilot study: Prospective, longitudinal and analytical cohort

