**Selection of participants:**

All persons that meet with inclusion criteria will be invited to participate in the research. The selection of participants will be done by each research group (UAH, US and UDC), through their contact with collaborators centers (specified below). In all cases, an information letter with the whole information of the project will be done to the chief or directors of those centers, to get the authorization to implement the research project in that entity.

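### The protocol names a paired t-test for comparing two independent groups of participants

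*Protocol*

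**What the plan says.** The protocol (section 4, Data analysis) first applies a normality check to choose between parametric and non-parametric tests. It then gives three sets of rules for comparing means.

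- **Two-level variables:** "The T- student paired test or the U-Mann Whitney will be applied to establish the possible differences of means, according different dicotomic variables". The sentence goes on to list what is compared: "in the assessment scales of FIM, PIADS, Walk tests and level of matching person – AT".
- **Variables with more than two levels:** "The ANOVA test or Kruskal – Wallis will be used in the cases of polycotomic variables".
- **Repeated measures:** a separate paragraph begins "To check the differences between related samples, with repeated measures (in the case of FIM scale and the scales of mobility". It covers the initial assessment and the 2- and 6-month follow-ups, and names a t-test (without the word paired) or Wilcoxon.

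The design is given as "Pilot study: Prospective, longitudinal and analytical cohort". On recruitment, the protocol says "All persons that meet with inclusion criteria will be invited to participate in the research". It describes no matching of participants and does not list the dichotomous variables. It states no sample size.

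**The concern.** A paired t-test works on one difference per unit, taken from two measurements on the same person or on a matched pair. Comparing FIM, PIADS, walk tests or person-technology match between the two levels of a participant characteristic compares different people, so no such differences exist. The two tests in the sentence therefore address different data structures, although the protocol chooses between them on normality alone.

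The sentence covers PIADS and the level of matching, which are the measures of the two main objectives of the MATCH subproject. Group comparisons of this kind also feed the last step of the Procedure, which looks for factors that help or hinder use of the device. An analyst who follows the text literally would have a test that either cannot be run or gives an answer that depends on how the rows happen to be sorted.

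**Working it through.** **1. Which comparison is meant?** The protocol gives no figure to reproduce, so the first check sets its own test choices side by side.

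| Comparison in the protocol | Parametric test named | Non-parametric test named | Structure implied by the non-parametric test |
|---|---|---|---|
| Two-level variable | paired t | Mann-Whitney | independent groups |
| Variable with more than two levels | ANOVA | Kruskal-Wallis | independent groups |
| Related samples, repeated measures | t (not labelled) | Wilcoxon | paired |

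Only the paired t entry in the first row is out of line. Could the dichotomous variable be time, before versus after? Four points speak against this:

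- Mann-Whitney is an independent-groups test.
- Kruskal-Wallis, its extension in the next sentence, is too.
- Before-after change has its own paragraph.
- PIADS is on the list for this sentence but not in the repeated-measures paragraph. The Procedure describes it as measuring the device's impact after implementation.

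**2. The two formulas.**

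- Independent: t = (m1 − m2) / sqrt(sp²(1/n1 + 1/n2)), with n1 + n2 − 2 degrees of freedom.
- Paired: t = mean(d) / (sd_d/√n), with n − 1 degrees of freedom. It needs one difference d per pair.

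**3. What happens if the paired test is used anyway?** All inputs here are assumptions: group sizes of 6 to 15, normal data, equal SDs and a two-sided 5% level.

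*Chance that the groups are equal in size.* For a characteristic present in half of participants, this is the binomial probability C(N, N/2) × 0.5^N.

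| Total N | 12 | 20 | 30 | 40 |
|---|---|---|---|---|
| Chance of an equal split | 22.6% | 17.6% | 14.4% | 12.5% |

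For odd totals it is zero. In all other cases, the named test cannot be applied to all participants.

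*Type I error.* Over 200,000 simulated data sets each for 6, 10 and 15 per group, with no true difference and arbitrary pairs, rejection rates were 4.98%, 4.98% and 4.96%. There is no inflation.

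*Power.* This uses the noncentral t with noncentrality d√(n/2), where d is the difference in SD units. Degrees of freedom are 2n − 2 (independent) against n − 1 (arbitrary pairs, zero correlation).

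| Difference | n per group | Independent | Paired | Loss (points) |
|---|---|---|---|---|
| 0.5 SD | 6 | 12.3% | 11.0% | 1.3 |
| 0.5 SD | 15 | 26.2% | 24.8% | 1.5 |
| 0.8 SD | 6 | 24.1% | 20.5% | 3.6 |
| 0.8 SD | 15 | 56.2% | 53.2% | 3.0 |
| 1.0 SD | 6 | 34.7% | 29.1% | 5.6 |
| 1.0 SD | 15 | 75.3% | 72.2% | 3.1 |

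Losses are taken before rounding. At 0.8 SD the loss peaks at 3.7 points, with 8 per group.

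*Dependence on row order.* Take one fixed data set with 10 per group, normal-quantile scores scaled to SD 1 and a shift of 1 SD. The independent test gives t = 1/√(2/10) = 2.24 on 18 degrees of freedom, p = 0.038. Over 20,000 random pairings of the same data, the paired p-value runs from 0.009 (5th percentile) to 0.106 (95th percentile). It is below 0.05 in 47% of pairings.

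**The case against.** The strongest reply is that this is a slip of wording. The surrounding text points to the right test, and the word paired looks misplaced: it sits on the group comparison and is absent from the repeated-measures paragraph. In practice the error would usually surface at once, because unequal groups give SPSS no pairs to analyse, and equal groups are the exception. An analyst would have to build arbitrary pairs deliberately to get the unstable p-value. The row-order example is also a constructed data set close to p = 0.05, where swings across the threshold look largest. Finally, the dichotomous variables are not named, so independence is inferred.

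Most of this stands as an argument about weight. It supports a low rating and a cautious reading of the figures. It does not make the sentence right: the text names a wrong test, which is different from leaving a detail to an analysis plan. The inference of independence is firm, because the protocol's own Mann-Whitney choice requires it and no matching is described. Inviting everyone eligible does not by itself rule out matching; it is only consistent with there being none.

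**Conclusion.** The concern holds, as a minor error. For two-level grouping variables and data that pass the normality check, the protocol names a test that does not fit the comparison. The Mann-Whitney, ANOVA and Kruskal-Wallis choices are sound. The repeated-measures paragraph is not wrong either, since related samples and Wilcoxon already imply the paired form.

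The practical harm is small. One branch of a pilot analysis is affected, the intended test can be inferred, false positives do not increase, and the power loss is between 1.3 and 5.6 points in the cases examined. The textual conclusion needs none of these numbers. They rest on assumed group sizes and effects, because the protocol gives none.

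**What to change.** In the protocol's Data analysis section, in the sentence on dichotomous variables, replace the paired Student t-test with the independent-samples t-test and keep Mann-Whitney as its alternative. As an optional clarification, the related-samples paragraph could say paired t-test or Wilcoxon signed-rank test.

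The cost is one phrase, or two with the optional change. Data collection, participants and the other analyses are unaffected.

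### For sparse tables the plan switches to the likelihood-ratio chi-square, another large-sample test that often exceeds the 5% level, and it triggers the switch on observed percentages instead of expected counts

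*Protocol*

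**What the plan says.** The rule is in the Data analysis part of section 4 (Methodology) of the protocol. To assess association between categorical variables, "chi-square will be applied, or likelihood ratio if the observed frequencies are lower than 5" per cent. The same part sets the error rate for all tests: "The level of significance to do the contrast of hypothesis is established to 5" per cent. It also names the software: "The analysis of the data will be done with the program SPSS v.24 for Windows".

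The design is given as "Pilot study: Prospective, longitudinal and analytical cohort". No sample size is stated; on recruitment the protocol says "All persons that meet with inclusion criteria will be invited to participate in the research". The protocol mentions no exact test and no criterion based on expected counts.

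**The concern.** A small-cell rule exists because Pearson's statistic follows the chi-square distribution only approximately, and the approximation weakens when expected counts are small. The remedy should therefore be a test that does not need the approximation. The likelihood-ratio statistic needs the same one. Moving to it in sparse tables replaces one large-sample test with another, and in most small 2x2 settings with a more liberal one.

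The trigger has a separate fault. It applies "if the observed frequencies are lower than 5" per cent, so it looks at what was observed, on a percentage scale. The adequacy of the approximation depends on expected counts.

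If the tables are small, which is plausible in a pilot, chance associations will be declared significant more often than the stated 5%. The last step of the Procedure uses the results to identify factors that help or hinder use of the device. Any of these examined as categorical associations would be exposed.

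**Working it through.** **Inputs from the protocol.** Significance level 5%; Pearson chi-square with a likelihood-ratio fallback; trigger of an observed frequency below 5% (all from Data analysis).

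**Assumed, because the protocol does not give them.** 2x2 tables with group sizes 8/8, 10/10, 15/15, 20/20, 30/30, 20/10, 25/5 and 40/20 (total 16 to 60). Common true proportion p of 0.05, 0.10, 0.15, 0.20, 0.25, 0.30, 0.40 or 0.50. That makes 8 × 8 = 64 settings. The trigger is read as any observed cell below 5% of the table total; reading it as a row percentage gives the same four rates for the rule in the table below.

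**Formulas.** With observed counts O and expected counts E = row total × column total / N:
- Pearson: X² = Σ(O − E)²/E
- Likelihood ratio: G² = 2 Σ O ln(O/E), with an empty cell contributing 0
- Both reject at 3.841 (1 degree of freedom).
- Type I error = the sum, over all tables that reject, of Bin(a; n₁, p) × Bin(c; n₂, p). Tables with an empty margin count as non-rejections.
- Mid-p = the Fisher p-value minus half the probability of the tables exactly as likely as the one observed.

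**One table by hand: 0/10 against 3/10.** The expected counts are 1.5 and 8.5 in each group.
- X² = 2 × 1.5²/1.5 + 2 × 1.5²/8.5 = 3.000 + 0.529 = 3.529, p = 0.060.
- G² = 2 × [10 ln(10/8.5) + 3 ln(3/1.5) + 7 ln(7/8.5)] = 2 × [1.625 + 2.079 − 1.359] = 4.691, p = 0.030.
- Fisher: 2 × C(10,3)/C(20,3) = 2 × 120/1140 = 0.21. Mid-p: 0.105.

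The empty cell triggers the fallback, so the plan declares this table significant. Neither Pearson nor the exact test does.

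**Type I error at nominal 5%, four settings with marked inflation**

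| Groups, p | Plan's rule | Pearson alone | Likelihood ratio with trigger changed to expected count < 5 |
|---|---|---|---|
| 10 vs 10, 0.20 | 7.3% | 3.0% | 8.7% |
| 15 vs 15, 0.15 | 7.9% | 4.1% | 7.9% |
| 20 vs 20, 0.10 | 8.5% | 3.9% | 8.5% |
| 25 vs 5, 0.30 | 8.8% | 4.2% | 8.8% |

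The last column shows that repairing the trigger alone does not help. The fallback is the main defect.

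**Settings without inflation.** The rule gives 4.9% at 10 vs 10, p = 0.10 and at 30 vs 30, p = 0.20. At 25 vs 5, p = 0.05 it gives 1.5%, while Pearson gives 7.1%.

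**Whole grid of 64 settings**

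| | Plan's rule | Pearson alone | Fisher or mid-p if any expected count < 5, else Pearson |
|---|---|---|---|
| Settings above 6% | 26 | 3 | 0 |
| Maximum | 9.1% | 7.7% | 5.5% |

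The rule is at or below 5% in 20 settings. It exceeds Pearson by at least 1 percentage point in 34 and is below Pearson in 3 (all 25 vs 5, p at most 0.15).

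A second grid of 63 scenarios, with some other group sizes (6+14, 10+20, 10+30), gives the same picture: the rule is above 5% in 42, with a maximum of 8.5%.

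**Larger tables.** For 3x3 tables with equal margins (40,000 simulated null tables each), likelihood ratio against Pearson is 9.8% against 4.4% at N = 20, 8.7% against 4.7% at N = 30, and 7.6% against 4.9% at N = 40.

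**The trigger fails in both directions.**
- 2/20 vs 5/20: the smallest cell is 2/40 = 5%, which is not below 5%, so chi-square is kept. The smallest expected count is 20 × 7/40 = 3.5.
- 9/100 vs 25/100: the smallest cell is 9/200 = 4.5%, so the fallback applies. The smallest expected count is 100 × 34/200 = 17.

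**The case against.** Five points can be made in the plan's favour.

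1. **Little hangs on these tests.** The objectives and outcome measures are scored scales, and no categorical endpoint is named. This stands. It limits the weight of the point but does not make the rule correct.
2. **The four settings tabulated are among the worse ones.** Over the 64 settings the rule's mean type I error is 5.8% and its median 5.6%, and in 23 settings it differs from Pearson by less than 0.5 percentage points. This also stands. The typical excess is under one point, and the large excess is confined to some sparse settings. Those are the tables for which the fallback was written.
3. **The sample size is unknown.** Several centres in three regions recruit, so larger tables are possible. At 50 vs 50 and p = 0.10 the rule gives 6.1%, and at 75 vs 75 it gives 5.2%. The size of the problem is therefore conditional on small tables.
4. **The trigger may be a loose rendering of a count below 5.** That may be so, but no text says it, and the corrected trigger with the likelihood ratio kept still gives 7.9% to 8.8% in the four settings.
5. **An exact test over-corrects.** Pearson-or-Fisher averages 2.3% over the grid and Pearson alone 4.1%, so simply deleting the fallback would be a simpler repair. It would improve on the present rule, but Pearson alone still exceeds 6% in 3 settings and reaches 7.7%. Mid-p is a middle course.

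**Conclusion.** The point holds. The fallback is unsuitable for its purpose, because it relies on the approximation that the rule is meant to avoid. The trigger is tied to the wrong quantity. Because the rule is written out in the protocol, this is not a detail left to a statistical analysis plan.

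Under the assumed table sizes, the rule typically runs somewhat above 5% and in unfavourable sparse settings reaches 8% to 9%, often about twice Pearson's rate. In a minority of settings there is no inflation, and in a few very unbalanced ones the rule is the more conservative. The principle does not depend on the assumptions; the magnitude does, since the protocol states no sample size. Only categorical associations are affected. The rule should be corrected, but it does not threaten the main outcome comparisons.

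**What to change.** Replace the sentence with one along these lines: *Association between categorical variables will be tested with Pearson's chi-square. If any expected count is below 5 in a 2x2 table, or more than 20% of expected counts are below 5 in a larger table, Fisher's exact test (Fisher-Freeman-Halton or a Monte Carlo exact test for larger tables) will be used.* Delete the likelihood-ratio option. If less conservatism is wanted, name the mid-p version in that sentence instead. Either way, fix the choice before the data are seen and confirm that the named software can produce it.

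The cost is one sentence and some power. Fisher's type I error is 0.8% to 2.2% in the four tabulated settings; mid-p gives 1.7% to 3.9%. Power in two illustrative cases:

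| Case | Pearson | New rule with Fisher | New rule with mid-p |
|---|---|---|---|
| 10 vs 10, 10% vs 60% | 66% | 47% | 66% |
| 15 vs 15, 10% vs 50% | 73% | 61% | 67% |

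Mid-p thus recovers all of the loss in the first case and about half in the second (67 − 61 = 6 of 73 − 61 = 12 points).

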## 5. Security and adverse effects

The damages or inconveniences that can be derived from the participation in this research are related with the time dedicated to the application of the questionnaires or scales (assessment phases), and during the test of AT.

During the development of the project, in concrete in the phase of elaboration and training of AT, all measures of security and personal protection required will be taken into account, to avoid possible damage derived from the use of materials and products. Moreover, research group will write a guideline of basic norms, cautions and recommendations that help in the use of AT by professionals and participants.

In the information that will be given to the participants (information sheet), these inconveniences will be noted, to offering the possibility to retire in any moment, if they detect any adverse effect during the development of the research.

## 6. Planning and Schedule:

Figure 1 offers a synthesis of a development of MATCH subproject, indicating the work packages derived from the specified tasks indicated in the procedure.

- T1: Protocol of assessment and intervention to implement. Definition and concretion of the process of informed consent.
- T2: Report of results from the initial assessment.
- T3: Report of improvements of the prototype to the access and use of assistive technology.
- T4: Registration of the implementation sessions with the AT.
- T5: Report from the detected improvements after the process of implementation of AT.
- T6: Report from the statistical analysis.
- T7: Descriptive protocol of applying of outcome measures in developments of artificial intelligence and robotics on AT.

[figure not shown]

Figure 1: Schedule of development of MATCH subproject.

## 7. Ethical Considerations, Protocols and Procedures:

All participants will receive a piece of research-related information about the project.

The informed consent form must be written in a language easily understood by the subjects, and it will be obtained from all participants or parents/legal tutor when involving children. There is no obligation to complete the experiment so that participants can withdraw from it at any time.

The treatment of biological samples or research with drugs or medical devices is not contemplated.

The performance of this study will respect the applicable regulations of ethics regard to research with humans. Mainly, the following legislative documents will be applied:

- Declaration of Helsinki: Ethical principles for medical research involving human subjects: General Principles (version 9th July 2018);
- European Commission. Ethics for researchers: Facilitating research excellence in FP7. Brussels: European Commission (2013);
- The Oviedo Convention: Protecting human rights in the biomedical field (4th April 1997);
- Ley 14/2007, de 3 de julio, de Investigación biomédica;
- Ley 3/2005, del 7 de marzo, de modificación de la Ley 3/2001, del 28 de mayo de 2001, reguladora del consentimiento informado y de la historia clínica de los pacientes.

For data protection we will follow “Regulation (EU) 2016/679 of the European Parliament and of the Council of 27 April 2016” and “Ley Orgánica 3/2018, del 5 de diciembre, de Protección de Datos Personales y garantía de los derechos digitales”.

The confidentiality of the data and the anonymity of the data will be maintained through pseudonymisation techniques. Once the study is finished, the data will be stored anonymously, with prior authorization from the participants.

The platform used to the registration and analysis of the results will be RedCAP (Research Electronic Data CAPture). “That is a secure web application for building and managing online surveys and databases. While REDCap can be used to collect virtually any type of data in any environment (including compliance with 21 CFR Part 11, FISMA, HIPAA, and GDPR), it is specifically geared to support online and offline data capture for research studies and operations.” The use of ReCAP will allow to codify previously the data, and guarded with specific passwords of very high privacy.

This research has been approved by the Galician Research Ethics Committee, with the reference number: 2020/597.

## **8. Expected Results Impact:**

- *Beyond state-of-the-art contributions*

The development of the project aims to go beyond the state of the art in new directions, such as the creation of low-cost assistive robotic platform to improve people's independence, and the possibility of detecting of emotional states in people with severe communication difficulties.

It is noted that people with disabilities have a lot of barriers to access and to do the activities that they want to do, most of the times conditioned by environmental factors and the lack of the correct support. The assistive technology is a possible solution to increase the participation and performance of this group, but actually, the available devices in the market don't meet

completely their needs, neither they take into account the individuality of each person with disability. With the development of AIR4DP, and with the contributions from all researchers' participants, especially in the application of outcome measures, the match between person and technology will be increased.

- *Socio-economic impact:*

The different analyzed reports on health and dependency show that the number of people with some disability, whether motor, sensorial, or cognitive, is sufficiently significant to justify the development of this project. Likewise, healthcare techniques and methods increasingly require ICT. Therefore, the development of new care techniques, in a relatively new area compared to other areas of research, will improve the quality of life of people with different types of disabilities. Likewise, the sometimes prohibitive price of many of the solutions on the market, imposes on the researchers, the task of making this type of system more accessible to the general public. We include in this group, both people with disabilities as individuals, as well as schools, medical centers, or institutions that perform this social initiative. Moreover, the other significant problem is that if AT is not adapted to individual needs or doesn't fit his/her expectations, it is not used.

The field of disability is a niche in which research, design, and innovation can be applied to a social purpose. In this sense, the document "Estrategia española sobre discapacidad. 2012-2020" of the Ministry of Health and Social Affairs, includes some figures and challenges that give an idea of the impact in this field. With regard to products and services linked to disability, this text said: "As for the existence of Information Society products or services accessible to DAPs, 82% agreed, although only 58% were able to name at least one accessible service or product, which demonstrates the gap between technologies and devices developed and their availability (at reasonable cost) in the market and therefore one of the objectives to be covered in this Strategy, even more so when 85% of those surveyed were optimistic that current or future Information Society technologies could solve the problems of DAPs". In this paragraph, we observe two of the parameters that are the starting point of the project presented. The users' perception that it is necessary to apply technology to the field of disability and, this application must be achieved at reasonable costs. In the conclusions of the document on disability strategies, it is mentioned in which areas and in which way the effort to implement solutions for disability will be expressed. It tells literally: "The identification of niches and market opportunities not yet covered or with scarce development should be promoted in this area, catalyzing new opportunities for research, development, and innovation, and fostering the connection between industry, business, and the university, as well as public-private partnerships". We understand that a proper connection between research, development, and the needs of disabled people can be an opportunity to create wealth and knowledge.

- *Transfer plan:*

The consortium is well aware of the great importance of transfer efforts in the context of attention to disability. Without transfer there is no help. That is why with this project we intend to bring aid to interested centers and patients. For doing so, research group have contacted with some institutions, which are interested in the outcomes of the project, and the most of them will participate actively in the performance of research project.

Another of the transfer tasks that we will explore, will consist in the elaboration and presentation of patents. As it can be seen in the trajectory of the research groups involved, they are all quite active in the granting of patents: UAH (4 patents), US (7 patents) and UDC (3 patents). We hope to be able to materialize some of the most relevant scientific findings in one or several patents, which can then be exploited by some companies interested in the sector of assistive technology.

